5.3 Duration of Therapy and Criteria for Study Discontinuation

In the absence of treatment delays due to adverse event(s), treatment may continue until one of the following criteria applies:

- Disease progression (unless the investigator judges that the patient is eligible for continuing beyond progression as stated in section 5.7),
- Intercurrent illness that prevents further administration of treatment,
- Patient decides to withdraw from the study, or
- General or specific changes in the patient's condition render the patient unacceptable for further treatment in the judgment of the investigator.
- Unacceptable adverse event(s) which include the following (see also section 6 and specific algorithms in Appendix C):
 - a) Any grade 4 events except as noted in item 'h' below.
 - b) Grade 3 drug-related autoimmune or inflammatory events including uveitis, pneumonitis, diarrhea, colitis, neurologic adverse events, hypersensitivity reaction, or infusion reaction of any duration requires discontinuation except as noted in item 'h' below:
 - c) Any grade 2 drug-related uveitis or eye pain or blurred vision that does not respond to topical therapy and does not improve to Grade 1 severity within the

re-treatment period OR requires systemic treatment.

- d) Patients requiring $> \text{two}$ dose delays for the same type of event (of grade 2 severity or above) should go off protocol therapy, unless the study doctor thinks that it is in the patient's best interest to remain in the study. The study doctor should also consult the Principal Investigator before continuing study treatment.
- e) Any adverse event, laboratory abnormality, or intercurrent illness which, in the judgment of the investigator, presents a substantial clinical risk to the subject with continued study drug dosing
- f) Tumor assessments should continue as per protocol even if dosing is interrupted. Any patients who require additional immune suppressive treatment beyond steroids should go off study treatment
- g) Any dosing interruption lasting > 6 weeks, with the following exceptions:

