Patients being tapered after high dose corticosteroids over one month followed by a two-week observation period will be allowed an additional two weeks to restart treatment (a maximum eight week interruption). Dosing interruptions > 6 weeks that occur for non-drug-related reasons may be allowed if approved by the Investigator. Prior to re-initiating treatment in a subject with a dosing interruption lasting > 6 weeks, the Principal Investigator must be consulted.
- h) The following exceptions do NOT require permanent study discontinuation:
 - Any other grade 3 non-skin, drug-related AE (other than grade 3 immune mediated event) lasting < 7 days including fatigue.
 - Any grade 3 or 4 drug-related laboratory abnormality or electrolyte abnormality, not associated with underlying organ pathology, that does not require treatment except for electrolyte replacements **does not** require treatment discontinuation.
 - Grade 3 or 4 amylase or lipase abnormalities that are not associated with diabetes mellitus (DM), associated liver or gall bladder inflammation clinical manifestations of pancreatitis and which decrease to 0 Grade 0 **may** resume study treatment when resolved.

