5.5 Criteria to Resume Treatment

5.5.1 General Criteria for Restarting Nivolumab:

Some patients may continue to benefit from treatment, maintaining or improving responses after progression including those treated with steroids.

Restarting applies only to grade 2 events and some grade 3 events (skin rash and thyroiditis). The section should emphasize stopping treatment and starting steroids earlier to obtain resolution with the possibility for restarting rather than waiting for higher grade events.

For non-autoimmune or non-inflammatory events patients may resume treatment with study drug when the drug-related AE(s) resolve to Grade ≤ 1 or baseline value, with the following exceptions:

- Patients may resume treatment in the presence of Grade 2 fatigue
- Evaluation to exclude any additional immune mediated events endocrine, GI, and liver / pancreas function as clinically indicated must be made prior to restarting.
- Non-drug-related toxicity including hepatic, pulmonary toxicity, diarrhea, or colitis, must have resolved to baseline before treatment is resumed.

If the criteria to resume treatment are met, the patient should restart treatment no sooner than the next scheduled time point per protocol. However, if the treatment is delayed past the next scheduled time point per protocol the treatment should resume at the earliest convenient point that is within the six week delay period.

If treatment is delayed for > 6 weeks, (> 8 weeks for patients on a steroid taper), the patient must be permanently discontinued from study therapy, except as specified in Section 5.3 (Duration of Therapy).

It should be emphasized that if adverse event occurs which requires treatment with steroids, it is preferable to withhold nivolumab and start steroids earlier to obtain resolution with the possibility for restarting nivolumab, rather than just waiting for higher grade events.

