6.1 Guideline for Nivolumab Related Adverse Events in General

ALL NON-IMMUNOLOGIC EVENTS*	Management/Next Dose for Nivolumab
≤ Grade 1	No change in dose
Grade 2	Hold until ≤ Grade 1 OR baseline Resume at same dose level.
Grade 3	Hold* until ≤ Grade 1 continue at investigator discretion
Grade 4	Off protocol therapy
* Not agent related, OR agent-related but non-immunologically mediated	
Recommended management: As clinically indicated	
ALL IMMUNOLOGIC EVENTS	Management/Next Dose for Nivolumab
≤ Grade 1	No change in dose
Grade 2	Hold until ≤ Grade 1 OR baseline* When resolved < or following steroids resume at same dose level.
Grade 3	Off protocol therapy (exceptions noted in 5.3)
Grade 4	Off protocol therapy
Recommended management: As clinically indicated	

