Grade ≥2 with suspected myocarditis	Hold dose.** Admit to hospital. Cardiology consult. Rule out MI and other causes of cardiac disease. Cardiac Monitoring. Cardiac Echo. Consider cardiac MRI and cardiac biopsy. Initiate high dose methylprednisolone. If no improvement within 24 hours, add either infliximab, ATG or tacrolimus. Consult algorithm for more details. Resume therapy if there is a return to baseline and myocarditis is excluded or considered unlikely.
Grade ≥2 with confirmed myocarditis	Off protocol therapy. Admit to CCU (consider transfer to nearest Cardiac Transplant Unit). Treat as above. Consider high dose methylprednisolone Add ATG or tacrolimus if no improvement. Off treatment.

*Including CHF, LV systolic dysfunction, Myocarditis, CPK, and troponin
 
**Patients with evidence of myositis without myocarditis may be treated according as “other event”
 
Note: The optimal treatment regimen for immune mediated myocarditis has not been established. Since this toxicity has caused patient deaths, an aggressive approach is recommended.
	

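### The cardiac row for suspected myocarditis in 6.2 permits restarting nivolumab after second-line immunosuppression or a grade 4 event, where 5.3 ends treatment

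*Combined protocol and SAP*

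**What the plan says.** The cardiac table in 6.2 has three rows: grade 1 or lower, grade 2 or higher with suspected myocarditis, and grade 2 or higher with confirmed myocarditis. The confirmed row ends protocol therapy. The suspected row holds the dose, admits the patient and starts high-dose methylprednisolone. It continues: "If no improvement within 24 hours, add either infliximab, ATG or tacrolimus". It closes with its own restart rule: "Resume therapy if there is a return to baseline and myocarditis is excluded or considered unlikely".

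Section 5.3 lists the unacceptable adverse events that end treatment.

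- Item (a): "Any grade 4 events except as noted in item 'h' below".
- Item (f): "Any patients who require additional immune suppressive treatment beyond steroids should go off study treatment". No exception is attached to it.
- Item (h) has a laboratory exception for grade 3 or 4 abnormalities that are "not associated with underlying organ pathology, that does not require treatment except for electrolyte replacements". It also has a separate exception for amylase and lipase. It names no cardiac exception.

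Both general tables in 6.1 send grade 4 events off protocol therapy. The first covers events described as "Not agent related, OR agent-related but non-immunologically mediated"; the second covers immunologic events.

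**The concern.** The suspected-myocarditis row starts at grade 2 and has no ceiling, so it includes grade 4. Its restart rule depends only on recovery to baseline and on how likely myocarditis is thought to be. It does not ask what treatment was needed or how severe the event was, and those are the two things on which 5.3(f) and 5.3(a) turn.

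Two sites could therefore manage the same patient in opposite ways, each citing the protocol. The permissive route re-exposes a patient whose event reached grade 4, or did not improve on high-dose steroids within a day, when myocarditis may have been judged only unlikely. Cardiac MRI and biopsy are things to consider in this row, not requirements. The note under the table itself records that this toxicity has been fatal.

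**Working it through.** No figure in the plan needs reproducing. The check is a comparison of texts.

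**1. Second-line immunosuppression.** The row adds infliximab, ATG or tacrolimus and then allows a restart. Under 5.3(f) the trigger is the treatment required, not the final diagnosis, so ruling out myocarditis does not by itself lift it. The routes in 5.5.2 and 6.3 for patients later found to have no autoimmune event cover corticosteroids only. This conflict is direct.

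**2. Grade 4.** The row allows a restart at any grade from 2 upward, whereas 5.3(a) stops treatment at grade 4. If myocarditis is excluded, the event may fall under the non-immunologic table in 6.1, but that table also ends therapy at grade 4. The general restart rule in 5.5.1 names grade 2 and certain grade 3 events and no grade 4 event. The possible exception is 5.3(h). The footnote to the cardiac table includes CPK and troponin, so an isolated grade 4 laboratory rise without organ pathology might qualify. The conflict therefore holds for grade 4 events outside the 5.3(h) laboratory exceptions.

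**3. Is it a deliberate exception?** The skin, liver, diarrhea/colitis, pneumonitis, other GI, fatigue, neurologic, endocrine and fever tables in 6.2 each take grade 4 off therapy. The amylase/lipase table qualifies this and repeats the matching exception from 5.3(h). Only the cardiac table has neither a grade 4 line nor a matching exception. Its header also refers to a combination with ipilimumab, although this is a single-agent trial, which suggests imported text. The row refers to an algorithm, but the title of Appendix C lists no cardiac one.

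**4. Does the delay limit prevent such restarts?** Under 5.3(g) and 6.3, a taper of about 4 weeks plus 2 weeks of observation is 4 + 2 = 6 weeks, against a maximum of 8. That leaves 8 − 6 = 2 weeks for the acute phase, second-line treatment and recovery before the taper. A restart is feasible. Any such time takes the interruption past 6 weeks, and 5.3(g) then requires consultation with the Principal Investigator.

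**5. Scale.** Section 13.2.1 caps accrual at 40. The documents give no rate for this group of patients. With an assumed per-patient rate p, the expected number is 40p and the chance of at least one is 1 − (1 − p)^40.

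| Assumed p | Expected patients | Chance of at least one |
|---|---|---|
| 0.1% | 0.04 | 3.9% |
| 0.5% | 0.20 | 18.2% |
| 1% | 0.40 | 33.1% |

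These rates are illustrations only.

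**The case against.** The strongest reply is that the row's silence is not permission. Section 5.3 lets treatment run only until one of its criteria is met, and it points to section 6, so the two can be read together. On that reading a patient who meets (a) or (f) is already off treatment and the restart step never arises. Sections 6.1 and 5.5.1 refer to 5.3 for exceptions, which supports 5.3 as the intended rule. But the cardiac row states its own restart rule without referring to 5.3, and nothing says which prevails. A clinician working from the table would not see the limit.

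It can also be said that a patient given infliximab empirically, with myocarditis later excluded, did not *require* it. Section 6.3 uses the word in that retrospective way, but only for corticosteroids. The argument has least force where myocarditis is merely judged unlikely.

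Three parts of the reply stand. The 5.3(h) laboratory exception may reach some grade 4 events. Consultation with the Principal Investigator is a real safeguard once the interruption passes 6 weeks. And the row permits re-dosing without compelling it, since 5.3(e) lets the investigator stop.

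A reader might also infer a grade 3 contradiction from the rule in 5.5.2 that stops nivolumab after steroids for grade 3 or higher. The documents do not settle that. Sections 5.5.2 and 6.3 allow a restart when no autoimmune event is found. Section 6.1 leaves non-immunologic grade 3 events to the investigator, and 5.3(h) exempts some short non-immune grade 3 events. Grade 3 is not part of this point.

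**Conclusion.** The row is wrong as written. It conflicts with 5.3(f) for patients who needed immunosuppression beyond steroids. It conflicts with 5.3(a) and 6.1 for grade 4 events outside the 5.3(h) laboratory exceptions. The conclusion rests on the text, with 5.3(f) read as turning on the treatment needed, and not on any assumed event rate.

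The numbers are small: few patients, possibly none, of at most 40. The reason to act is the seriousness of a wrong re-exposure. A reader might infer that every grade 4 restart under this row is forbidden, or that the trial's result is at risk. Neither follows: 5.3(h) leaves room for some laboratory events, and the response endpoint and decision rule in 13.1 do not depend on this row. The summary of changes for Amendment 4 also mentions cardiac discontinuation, but it is not relied on here.

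**What to change.** In this row only, replace the last sentence with: *Resume therapy, subject to 5.3 and 5.5, only if there is a return to baseline, myocarditis is excluded or considered unlikely, and no immunosuppression beyond steroids was required (5.3(f)). Grade 4 events: off protocol therapy, except as noted in 5.3(h).*

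Two broader changes should be avoided. Naming grade 3 as eligible for restart would write in a cardiac allowance that 5.5.1 does not list. A general statement that 5.3 overrides every table in 6.2 could cut across the grade 3 rash allowance in 5.5.1, 5.5.2 and the skin table.

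The cost is one reworded row in an amendment, with no statistical consequence. The downside is that a rare patient cleared of myocarditis after second-line immunosuppression or a grade 4 event could not be re-dosed, which 5.3 already requires.

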6.3 Guideline for Steroid Use

If treatment is delayed > 6 weeks, > 8 weeks for patients on high dose steroids with recommended 4 weeks taper and 2 week observation, the patient must be permanently discontinued from study therapy, except as specified in Section 5.5 (Criteria to Resume Treatment.)

Patients requiring a delay of > 6 weeks, > 8 weeks for patients on high dose steroids with required 4 weeks minimal taper and 2 weeks observation, should go off protocol therapy. Patients requiring $>$ two dose delays for the same event should go off protocol therapy.

Prior to starting corticosteroids or hormone replacement for any reason, appropriate endocrine testing including cortisol, ACTH, TSH and T4 must be obtained to document baseline.

Patients may be dose-delayed for evaluation and restarted depending on results.

Any patient started on corticosteroids initially who is determined to not require steroids treatment for an autoimmune adverse event may resume therapy after a 2 week observation period without further symptoms at the discretion of the PI or investigator.

7. ADVERSE EVENTS: LIST AND REPORTING REQUIREMENTS

Adverse event (AE) monitoring and reporting is a routine part of every clinical trial. The following list of AEs (Section 7.1) and the characteristics of an observed AE (Section 7.2) will determine whether the event requires expedited reporting via the CTEP Adverse Event Reporting System (CTEP-AERS) **in addition** to routine reporting.

7.1 Comprehensive Adverse Events and Potential Risks List (CAEPR)

Comprehensive Adverse Events and Potential Risks list (CAEPR) for BMS-936558 (Nivolumab, MDX-1106, NSC 748726)

The Comprehensive Adverse Events and Potential Risks list (CAEPR) provides a single list of reported and/or potential adverse events (AE) associated with an agent using a uniform presentation of events by body system. In addition to the comprehensive list, a subset, the Specific Protocol Exceptions to Expedited Reporting (SPEER), appears in a separate column and is identified with bold and italicized text. This subset of AEs (SPEER) is a list of events that are protocol specific exceptions to expedited reporting to NCI (except as noted below). Refer to the 'CTEP, NCI Guidelines: Adverse Event Reporting Requirements'
http://ctep.cancer.gov/protocolDevelopment/electronic_applications/docs/aeguidelines.pdf for further clarification. Frequency is provided based on 2069 patients. Below is the CAEPR for BMS-936558 (Nivolumab, MDX-1106).

NOTE: Report AEs on the SPEER **ONLY IF** they exceed the grade noted in parentheses next to the AE in the SPEER. If this CAEPR is part of a combination protocol using multiple investigational agents and has an AE listed on different SPEERs, use the lower of the grades to determine if expedited reporting is required.

Version 2.2, November 15, 2016¹

Adverse Events with Possible Relationship to BMS-936558 (Nivolumab, MDX-1106) (CTCAE 4.0 Term) [n= 2069]			Specific Protocol Exceptions to Expedited Reporting (SPEER)
Likely (>20%)	Less Likely (<=20%)	Rare but Serious (<3%)	
BLOOD AND LYMPHATIC SYSTEM DISORDERS			
	Anemia		Anemia (Gr 2)
CARDIAC DISORDERS			
		Cardiac disorders - Other (cardiomyopathy)	
		Myocarditis	
		Pericardial tamponade ²	
		Pericarditis	
ENDOCRINE DISORDERS			
	Adrenal insufficiency		
	Endocrine disorders - Other (hypophysitis)		
	Hyperthyroidism		
	Hypothyroidism		
EYE DISORDERS			
		Eye disorders - Other (diplopia)	
		Eye disorders - Other (Graves ophthalmopathy)	
		Eye disorders - Other (optic neuritis retrobulbar)	
	Uveitis		
GASTROINTESTINAL DISORDERS			
	Abdominal pain		Abdominal pain (Gr 2)

Adverse Events with Possible Relationship to BMS-936558 (Nivolumab, MDX-1106) (CTCAE 4.0 Term) [n= 2069]			Specific Protocol Exceptions to Expedited Reporting (SPEER)
Likely (>20%)	Less Likely (<=20%)	Rare but Serious (<3%)	
	Colitis		
		Colonic perforation	
	Diarrhea		Diarrhea (Gr 2)
	Dry mouth		Dry mouth (Gr 2)
		Gastritis	
	Nausea		Nausea (Gr 2)
	Pancreatitis ³		
GENERAL DISORDERS AND ADMINISTRATION SITE CONDITIONS			
Fatigue			Fatigue (Gr 2)
	Fever		Fever (Gr 2)
	Infusion related reaction ⁴		
	Injection site reaction		Injection site reaction (Gr 2)
IMMUNE SYSTEM DISORDERS			
		Allergic reaction	
		Autoimmune disorder ⁵	
		Cytokine release syndrome ⁶	
		Immune system disorders - Other (GVHD in the setting of allograft transplant) ⁷	
		Immune system disorders - Other (sarcoid granuloma) ⁵	
INVESTIGATIONS			
	Alanine aminotransferase increased		Alanine aminotransferase increased (Gr 2)
	Aspartate aminotransferase increased		Aspartate aminotransferase increased (Gr 2)
	Blood bilirubin increased		Blood bilirubin increased (Gr 2)
	Creatinine increased		
	Lipase increased		
	Lymphocyte count decreased		Lymphocyte count decreased (Gr 2)
	Neutrophil count decreased		
	Platelet count decreased		
	Serum amylase increased		
METABOLISM AND NUTRITION DISORDERS			
	Anorexia		
		Hyperglycemia	Hyperglycemia (Gr 2)
		Metabolism and nutrition disorders - Other (diabetes mellitus with ketoacidosis)	
MUSCULOSKELETAL AND CONNECTIVE TISSUE DISORDERS			
	Arthralgia		
		Musculoskeletal and connective tissue disorder - Other (polymyositis)	
		Musculoskeletal and connective tissue disorder - Other (rhabdomyolysis)	

Adverse Events with Possible Relationship to BMS-936558 (Nivolumab, MDX-1106) (CTCAE 4.0 Term) [n= 2069]			Specific Protocol Exceptions to Expedited Reporting (SPEER)
Likely (>20%)	Less Likely (<=20%)	Rare but Serious (<3%)	
		Myositis	
NERVOUS SYSTEM DISORDERS			
		Encephalopathy	
		Facial nerve disorder ⁵	
		Nervous system disorders - Other (demyelination myasthenic syndrome)	
		Nervous system disorders - Other (encephalitis)	
		Nervous system disorders - Other (Guillain-Barre syndrome) ⁵	
		Nervous system disorders - Other (meningoencephalitis)	
		Nervous system disorders - Other (meningoradiculitis)	
		Nervous system disorders - Other (myasthenia gravis) ⁵	
		Nervous system disorders - Other (myasthenic syndrome)	
		Peripheral motor neuropathy	
		Peripheral sensory neuropathy	
RENAL AND URINARY DISORDERS			
		Acute kidney injury	
RESPIRATORY, THORACIC AND MEDIASTINAL DISORDERS			
		Pleural effusion	
		Pneumonitis	
		Respiratory, thoracic and mediastinal disorders - Other (bronchiolitis obliterans with organizing pneumonia)	
SKIN AND SUBCUTANEOUS TISSUE DISORDERS			
		Erythema multiforme	
		Pruritus	Pruritus (Gr 2)
		Rash maculo-papular	Rash maculo-papular (Gr 2)
		Skin hypopigmentation	
		Skin and subcutaneous disorders - Other (Sweet's Syndrome)	

¹This table will be updated as the toxicity profile of the agent is revised. Updates will be distributed to all Principal Investigators at the time of revision. The current version can be obtained by contacting [contact]. Your name, the name of the investigator, the protocol and the agent should be included in the e-mail.

²Pericardial tamponade may be related to possible inflammatory reaction at tumor site.

³Pancreatitis may result in increased serum amylase and/or more frequently lipase.

⁴Infusion reactions, including high-grade hypersensitivity reactions which have been observed following administration of nivolumab, may manifest as fever, chills, shakes, itching, rash, hypertension or hypotension, or difficulty breathing during and immediately after administration of nivolumab.

⁵BMS-936558 (Nivolumab, MDX-1106) being a member of class of agents involved in the inhibition of “immune checkpoints”, may result in severe and possibly fatal immune-mediated adverse events probably due to T-cell activation and proliferation. This may result in autoimmune disorders that can include (but are not limited to) autoimmune hemolytic anemia, acquired anti-factor VIII immune response, autoimmune aseptic meningitis, autoimmune hepatitis, autoimmune nephritis, autoimmune neuropathy, autoimmune thyroiditis, bullous pemphigoid, exacerbation of Churg-Strauss Syndrome, drug rash with eosinophilia systemic symptoms [DRESS] syndrome, facial nerve disorder (facial nerve paralysis), limbic encephalitis, hepatic failure, pure red cell aplasia, pancreatitis, ulcerative and hemorrhagic colitis, endocrine disorders (e.g., autoimmune thyroiditis, hyperthyroidism, hypothyroidism, autoimmune hypophysitis/hypopituitarism, thyrotoxicosis, and adrenal insufficiency), sarcoid granuloma, myasthenia gravis, polymyositis, and Guillain-Barre syndrome.

⁶Cytokine release syndrome may manifest as hemophagocytic lymphohistiocytosis with accompanying fever and pancytopenia.

⁷Complications including hyperacute graft-versus-host disease (GVHD), some fatal, have occurred in patients receiving allo stem cell transplant (SCT) after receiving BMS-936558 (Nivolumab, MDX-1106). These complications may occur despite intervening therapy between receiving BMS-936558 (Nivolumab, MDX-1106) and allo-SCT.

Adverse events reported on BMS-936558 (Nivolumab, MDX-1106) trials, but for which there is insufficient evidence to suggest that there was a reasonable possibility that BMS-936558 (Nivolumab, MDX-1106) caused the adverse event:

CARDIAC DISORDERS - Atrial fibrillation; Atrioventricular block complete; Heart failure; Ventricular arrhythmia

EAR AND LABYRINTH DISORDERS - Vestibular disorder

EYE DISORDERS - Eye disorders - Other (iritocyclitis); Optic nerve disorder

GASTROINTESTINAL DISORDERS - Constipation; Duodenal ulcer; Flatulence; Gastrointestinal disorders - Other (mouth sores); Mucositis oral; Vomiting

GENERAL DISORDERS AND ADMINISTRATION SITE CONDITIONS - Chills; Edema limbs; Malaise; Pain

HEPATOBILIARY DISORDERS - Bile duct stenosis

IMMUNE SYSTEM DISORDERS - Anaphylaxis; Immune system disorders - Other (autoimmune thrombotic microangiopathy); Immune system disorders - Other (limbic encephalitis)

INFECTIONS AND INFESTATIONS - Bronchial infection; Lung infection; Sepsis; Upper respiratory infection

INVESTIGATIONS - GGT increased; Investigations - Other (blood LDH increased); Investigations - Other (protein total decreased); Investigations - Other (WBC count increased); Lymphocyte count increased; Weight loss

METABOLISM AND NUTRITION DISORDERS - Dehydration; Hyperuricemia; Hypoalbuminemia; Hypocalcemia; Hyponatremia; Hypophosphatemia

MUSCULOSKELETAL AND CONNECTIVE TISSUE DISORDERS - Back pain; Musculoskeletal and connective tissue disorder - Other (musculoskeletal pain); Musculoskeletal and connective tissue disorder - Other (polymyalgia rheumatica); Myalgia; Pain in extremity

NEOPLASMS BENIGN, MALIGNANT AND UNSPECIFIED (INCL CYSTS AND POLYPS) - Neoplasms benign, malignant and unspecified (incl cysts and polyps) - Other (histiocytic necrotizing lymphadenitis)

NERVOUS SYSTEM DISORDERS - Dizziness; Headache; Intracranial hemorrhage
PSYCHIATRIC DISORDERS - Insomnia
RENAL AND URINARY DISORDERS - Hematuria; Renal and urinary disorders - Other (tubulointerstitial nephritis)
RESPIRATORY, THORACIC AND MEDIASTINAL DISORDERS - Bronchospasm; Cough; Dyspnea; Hypoxia
SKIN AND SUBCUTANEOUS TISSUE DISORDERS - Alopecia; Dry skin; Hyperhidrosis; Pain of skin; Periorbital edema; Photosensitivity; Rash acneiform; Skin and subcutaneous tissue disorders - Other (rosacea); Toxic epidermal necrolysis
VASCULAR DISORDERS - Flushing; Hypertension; Hypotension; Vasculitis

Note: BMS-936558 (Nivolumab, MDX-1106) in combination with other agents could cause an exacerbation of any adverse event currently known to be caused by the other agent, or the combination may result in events never previously associated with either agent.

